7.1 RISKS TO CONFIDENTIALITY OF STUDY SUBJECTS

Patient confidentiality will be maintained under HIPAA Privacy Rules by de-identifying personal subject information and following the applicable Good Clinical Practice guidelines for clinical research.

8 ADVERSE EVENTS

Subject safety is of the utmost importance. Each investigator has the responsibility for the safety of the subjects under his/her care. Throughout the course of the study, all significant study related adverse events will be documented and monitored on an adverse event CRF/eCRF, including seriousness, severity, treatment, and relationship to the study device/procedure.

8.1 ADVERSE EVENT

An adverse event (AE) is any undesirable experience (sign, symptom, illness, abnormal laboratory value, or other medical event) occurring to a patient, whether or not considered related to the study product(s) prescribed as part of the protocol, that is identified or worsens during a clinical study. Any current condition that is recorded as a pre-existing condition, unless there is a change in nature, severity, or degree of incidence, is not an AE.

8.2 SERIOUS ADVERSE EVENT

A serious adverse event (SAE) is an AE that:

- Led to death,
- Led to serious deterioration in the health of the subject, that resulted in
 - 1) a life-threatening illness or injury, or
 - 2) a permanent impairment of a body structure or a body function, or
 - 3) in-patient or prolonged hospitalization, or
 - 4) medical or surgical intervention to prevent permanent life-threatening illness or injury or permanent impairment to a body structure or a body function.
- Led to fetal distress, fetal death or a congenital anomaly or birth defect

The investigator must determine whether each event meets the definition of a “serious” adverse event. All SAEs must be reported on the CRFs/eCRFs, regardless of relationship, or lack thereof, to the device/procedure.

All other events that are considered medically serious by the investigator should be reported immediately to the study sponsor.

Planned hospitalization for a pre-existing condition, or a procedure required by the protocol, without serious deterioration in health, is not considered an SAE.

8.2.1 Serious Adverse Device Effect

A serious adverse device effect (SADE) is an adverse device effect that has resulted in any of the consequences characteristic of a serious adverse event. An anticipated serious adverse

device effect (ASADE) is an effect which by its nature, incidence, severity or outcome has been identified in the risk analysis report.

8.2.2 Unanticipated Adverse Device Effect

An unanticipated adverse device effect (UADE) means any serious adverse effect on health or safety or any life-threatening problem or death caused by, or associated with, a device, if that effect, problem, or death was not previously identified in nature, severity, or degree of incidence in the study protocol or application (including a supplementary plan or application), or any other unanticipated serious problem associated with a device that relates to the rights, safety, or welfare of subjects. (21 CFR 812.3 (s)).

8.3 SEVERITY OF ADVERSE EVENTS

The severity of an AE is a qualitative judgment of the degree of intensity, as determined by the Investigator or as reported by the subject. The severity of the AE should be evaluated according to the following scale:

- **Mild:** No limitation of usual activities, no therapy or only symptomatic therapy required to treat the injury or illness.
- **Moderate:** Some limitation of usual activities or specific therapy is required.
- **Severe:** Inability to carry out usual activities, hospitalization, emergency treatment, life threatening events, or death.

The assessment of severity should be made independent of the relationship to the investigational device and therapy or the seriousness of the event.

Only those possibly related or definitely related will be reported in EDC for this study unless the AE is determined to be an SAE. All SAEs will be reported in EDC regardless of relationship, or lack thereof, to the study devices/procedures.

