8.5 REPORTING OF ADVERSE EVENTS

Subjects will be carefully monitored during the study for possible AEs. Any AE observed should be fully evaluated by the investigator. Collection of related AEs and all SAEs will

commence from the time the patient has the study procedure. Routine collection of AEs will continue until Study Completion or Termination visit.

At each study visit, the investigator will assess whether any device/procedure related AEs or SAEs have occurred. Subjects may report AEs occurring at any other time during the study.

All subjects experiencing AEs, whether considered associated with the device and/or procedure or not, must be monitored until the symptoms subside and have returned to baseline or until there is a satisfactory explanation for the changes observed. All AEs will be documented on the Adverse Event CRF, when the investigator concludes the event to be either possibly or definitely related to the study device/procedure, and/or the AE is serious. The event term, start and stop date and severity will be documented, along with the investigator's opinion of the nature of the causal relationship between the event and the device/procedure.

UADEs have special reporting requirements. investigator and sponsor will follow adverse device effects reporting requirements per CFR Title 21 Part 803:

Investigator Report: If a subject experiences an UADE, the investigator must notify sponsor within 24-hours of receiving knowledge of the event, and the IRB/EC as soon as possible, but no later than the deadline specified by IRB/Ethics Committee (EC) reporting policy.

Sponsor Report: UADEs will be reported to FDA, all reviewing IRB/ECs, and participating investigators as soon as possible, but no later than 10 working days, after receiving notice of the UADE(s).

As with any AE outside of the study, all AEs should be followed up until resolution or until the investigator judges that further follow-up is not necessary.

The investigator must follow their local IRB policy for AE reporting. Such events may be reportable to the FDA under the Medical Device Reporting Regulation. Product complaints related to the MILD devices will be documented and investigated per Vertos quality policy.

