10.3 CLINICAL EVENTS ADJUDICATOR (CEA)

The CEA will be an individual who is independent of the Investigational Sites. The CEA will be responsible for the review and validation of all complications that occur over the course of the Study and the subsequent classification of these complications as related to the device or procedure. The CEA will review all complications and adjudicate them as defined in Section 8: Adverse Events. The CEA can request additional source documentation and any available imaging to assist with adjudication.

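### For non-serious events the site's relatedness call decides what the adjudicator sees, so adjudication can only lower the related count

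*Combined protocol and SAP*

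**What the plan says.** Recording. The rule printed at the end of section 8.3 is: "Only those possibly related or definitely related will be reported in EDC for this study unless the AE is determined to be an SAE". Section 8.5 repeats it and names who applies it: "All AEs will be documented on the Adverse Event CRF, when the investigator concludes the event to be either possibly or definitely related", or when the event is serious.

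Serious events. These are exempt from the filter: "All SAEs will be reported in EDC regardless of relationship, or lack thereof, to the study devices/procedures". The site makes the seriousness decision under section 8.2: "The investigator must determine whether each event meets the definition of a" serious AE.

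Adjudication. Section 10.3 states: "The CEA will be responsible for the review and validation of all complications that occur over the course of the Study". It then has the CEA classify these complications as device- or procedure-related, using the definitions in section 8.

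Reporting. Section 9.2 names two safety outputs. One is the incidence of serious device- or procedure-related AEs as adjudicated, tabulated by randomized group. The other is a summary of the AEs that were reported.

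The public copy goes from 8.3 to 8.5, so the filter printed under 8.3 may belong to an 8.4 that is not shown. Section 8.5 is the firmer reference, and it carries the same rule.

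**The concern.** Sections 8.5 and 10.3 give the same decision to two parties in sequence, and the first party's answer determines whether the second is asked. Section 8.1 defines an AE without regard to relatedness, and 10.3 gives the CEA all complications. The CEA cannot carry out that task for non-serious events if the site has already removed those it considers unrelated.

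The site is not a neutral filter. The control arm is CMM without MILD, and the site investigator chooses the CMM, so the site knows the assignment. Several MILD risks in Table 2, such as paresthesia and radiculopathy, can resemble symptoms of the underlying stenosis, so attributing them to the disease is a plausible error.

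At stake is how far a reader can rely on the non-serious safety profile, in a study whose objective (section 4) includes a comprehensive safety evaluation.

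**Working it through.** The plan states no figure on this point, so there is nothing to reproduce. The check follows each type of event through sections 8.2, 8.3, 8.5 and 10.3.

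| Site's call | On AE form / EDC? | Reaches CEA? | What the CEA can do |
|---|---|---|---|
| Non-serious, possibly or definitely related | Yes | Yes | Confirm, or change to unrelated |
| Non-serious, unrelated | No | No route described | Nothing |
| Serious, any relatedness | Yes | Yes | Change in either direction |

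The one-way effect is confined to non-serious events. For an event called serious, the relatedness filter loses nothing. An event that is truly serious and related drops out only if the site wrongly calls it both non-serious and unrelated.

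Other safeguards in the visible text:

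- Section 10.3 lets the CEA request source documents to help adjudicate, which presupposes an event already submitted.
- Section 12 has the sponsor screen the case report forms for potential AEs, but the filter keeps these events off the AE form.
- Section 10.2 has the medical monitor review study data and safety.
- Section 11.4 has the site assess whether a missed visit reflects a device or procedure problem.

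Any of the last three might bring an event to light. None is described as a route to the CEA.

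For scale only, an illustration in the MILD arm:

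- n = 75, from up to 150 subjects (section 5.1) allocated 1:1 (section 6.2): 150 / 2 = 75.
- p = share of subjects with a truly related non-serious event. Assumed 5%, 10%, 20%.
- m = share of those that the site calls unrelated. Assumed 10%, 20%, 30%.
- Expected subjects missed = n × p × m.

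| p | m = 10% | m = 20% | m = 30% |
|---|---|---|---|
| 5% | 0.375 | 0.75 | 1.125 |
| 10% | 0.75 | 1.5 | 2.25 |
| 20% | 1.5 | 3.0 | 4.5 |

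At p = 10% and m = 20%, 75 × 0.10 = 7.5 subjects have such an event and 7.5 × 0.20 = 1.5 are missed. The rate that can be reported falls from 10% to 6.0 / 75 = 8%. The chance of missing at least one subject is 1 − (1 − 0.10 × 0.20)^75 = 1 − 0.98^75 = 78%. Even perfect judgement by the CEA recovers none of these.

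**The case against.** The strongest reply is that restricted collection is deliberate and consistent. Sections 8.3, 8.5, 11.6 and 13.4 all centre on related AEs and SAEs, and section 7 describes the study as an evaluation of marketed treatments. A summary of reported AEs claims to cover only what was reported. The threshold is also low: possible relatedness is enough, so a site must rule out even a possible link before an event is lost. All of this stands and limits the loss. It does not reconcile the filter with 10.3 or give the CEA a way to correct the site in the other direction.

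A reader might infer that the adjudicated safety endpoint itself is biased downward. The documents do not support that. The endpoint counts serious related AEs, all SAEs enter EDC whatever the site thinks of relatedness, and the CEA can move them either way.

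A reader might also infer that under-reporting has been shown, or that the assessor performed the procedure. The first rests on rates that the documents do not give, and the second is possible but not stated.

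Finally, sending every spinal, lower-limb or neurological event to the CEA would, in claudication patients, collect much ordinary fluctuation of the disease. That objection is sound, and the fix is limited accordingly.

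**Conclusion.** The point holds for non-serious AEs. The site decides relatedness before the CEA sees anything, 10.3 describes a wider remit than the data flow allows, and adjudication can only reduce the number of related non-serious events. The affected outputs are the general AE summary in 9.2 and any non-serious related rate derived from the same data. The formal serious-AE endpoint is affected only if a site errs on both seriousness and relatedness for the same event.

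The size is unknown. Under the assumed ranges, about 0.4 to 4.5 of 75 MILD subjects would be missed, and these figures depend entirely on the assumed p and m. The conclusion also rests on the visible text: a missing 8.4 could define the relatedness categories further, but 8.5 already states the filter and who applies it. The change is worth making for the credibility of the safety report. The primary efficacy analysis is not touched.

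**What to change.** Amend 8.3 and 8.5 so that, in both arms, any new or worsened AE matching a risk listed in Table 2 is entered in EDC whatever the site's view of relatedness. Exclude simple inadequate pain relief, which the efficacy scales capture. Keep the site's opinion as a data field, send these events to the CEA, and use the CEA's classification in the tables. Reword 10.3 so that the CEA's remit matches this scope.

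If the sponsor keeps the present filter, the least it should do is limit 10.3 to reported events and state that relatedness of non-serious AEs is screened by the investigator. That removes the contradiction but leaves the one-way effect.

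The cost is added ascertainment at sites, data entry and CEA review for about 150 subjects, and a higher reported count of non-serious AEs. Section 8.5 already says "All subjects experiencing AEs, whether considered associated with the device and/or procedure or not, must be monitored", which reduces the burden but does not remove it: the visit assessment in 8.5 asks only about related AEs and SAEs, so systematic questioning about the Table 2 events would be partly new work. No new role is needed, since the CEA is already in place.

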8.5 REPORTING OF ADVERSE EVENTS

Subjects will be carefully monitored during the study for possible AEs. Any AE observed should be fully evaluated by the investigator. Collection of related AEs and all SAEs will

commence from the time the patient has the study procedure. Routine collection of AEs will continue until Study Completion or Termination visit.

At each study visit, the investigator will assess whether any device/procedure related AEs or SAEs have occurred. Subjects may report AEs occurring at any other time during the study.

All subjects experiencing AEs, whether considered associated with the device and/or procedure or not, must be monitored until the symptoms subside and have returned to baseline or until there is a satisfactory explanation for the changes observed. All AEs will be documented on the Adverse Event CRF, when the investigator concludes the event to be either possibly or definitely related to the study device/procedure, and/or the AE is serious. The event term, start and stop date and severity will be documented, along with the investigator's opinion of the nature of the causal relationship between the event and the device/procedure.

UADEs have special reporting requirements. investigator and sponsor will follow adverse device effects reporting requirements per CFR Title 21 Part 803:

Investigator Report: If a subject experiences an UADE, the investigator must notify sponsor within 24-hours of receiving knowledge of the event, and the IRB/EC as soon as possible, but no later than the deadline specified by IRB/Ethics Committee (EC) reporting policy.

Sponsor Report: UADEs will be reported to FDA, all reviewing IRB/ECs, and participating investigators as soon as possible, but no later than 10 working days, after receiving notice of the UADE(s).

As with any AE outside of the study, all AEs should be followed up until resolution or until the investigator judges that further follow-up is not necessary.

The investigator must follow their local IRB policy for AE reporting. Such events may be reportable to the FDA under the Medical Device Reporting Regulation. Product complaints related to the MILD devices will be documented and investigated per Vertos quality policy.

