5.2 STUDY DURATION

Subjects who meet the inclusion / exclusion criteria may be enrolled

The screening/baseline visit and CMM procedures may take place at the investigator's medical office. MILD procedures will be performed at the treating ambulatory surgery centers or hospital. Subjects will be requested to return for follow-up at a location designated by research staff.

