6 STUDY PROCEDURE

6.1 PATIENT SELECTION AND BASELINE VISIT

Selection begins with a screening process when the patient is examined by their physician. Once the investigator has determined that the patient is potentially eligible for treatment in the study, the consent should be reviewed with the patient, questions answered, and the patient should be asked to sign the Informed Consent document. The eligibility of a patient for treatment in this study will be determined after all enrollment criteria have been satisfied.

completed, all enrollment criteria are met and an informed consent signed, will the patient be officially enrolled into the study.

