6.2 RANDOMIZATION

Subjects will be randomly assigned in equal number (1:1) to one of two treatment arms: 1) MILD procedure plus CMM or 2) CMM only.

Based on the information provided, the system will automatically generate the assigned treatment.

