6.4 TREATMENT

Subjects will be treated with either MILD plus CMM or CMM alone based on randomization results.

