6.9 STUDY SCHEDULE

At baseline, prior therapies will be documented, including frequency, duration, type of therapy
Documentation of analgesic use for the treatment of neurogenic claudication symptoms will
include frequency and dosage.

Device/Procedure-related unexpected complications and significant adverse events will be documented throughout the study period.

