13.4 ADVERSE EVENT REPORTING

It is the investigator's responsibility to promptly report all device/procedure related AEs and/or SAEs occurring during the study to the SPI and to inform their IRB as required.

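### Section 8.5 starts collection of related AEs and all SAEs at a study procedure that follows randomization and is not defined in the visible text, so the window omits earlier SAEs and may differ by arm

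*Combined protocol and SAP*

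**What the plan says.** **Start of collection.** Under Section 8.5, collection of related AEs and of every SAE will "commence from the time the patient has the study procedure". It ends at the completion or termination visit.

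**Order of events.** Section 6.2: "Subjects will be randomly assigned in equal number (1:1) to one of two treatment arms". Section 6.4: "Subjects will be treated with either MILD plus CMM or CMM alone based on randomization results". Section 6.4.2 leaves the choice of CMM therapy to the investigator over the course of the study and gives no visible index date.

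**Other reporting rules.**
- Section 8.2: "All SAEs must be reported on the CRFs/eCRFs, regardless of relationship, or lack thereof, to the device/procedure".
- Section 13.4: the investigator must "promptly report all device/procedure related AEs and/or SAEs occurring during the study to the SPI".
- Section 6.9: "Device/Procedure-related unexpected complications and significant adverse events will be documented throughout the study period".

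**Analysis.** Section 9 opens by covering treated subjects in the safety evaluation, then sets out analysis by randomized assignment. Section 9.2 tabulates the adjudicated serious device/procedure-related events by randomized group and promises a summary of all AEs reported.

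**The concern.** A safety comparison between randomized arms needs one time zero for both. Section 8.5 uses a later event instead, and the timing of that event depends on the arm. One arm has a scheduled operation, while the other has therapies chosen as the study goes on.

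Two things are at stake. First, Section 4 promises a comprehensive evaluation of safety, and a site that follows the start rule in Section 8.5 may omit an SAE that a site following Section 13.4 would report. Second, any all-cause SAE comparison between arms could rest on windows of unequal length.

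**Working it through.** The plan gives no figure on this point, so there is none to reproduce. The check is mainly a comparison of the texts.

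1. **Is there an interval before treatment?** Sections 6.2 and 6.4 put treatment after randomization. Section 5.2 says "MILD procedures will be performed at the treating ambulatory surgery centers or hospital", while the baseline visit and CMM may take place at the investigator's office. A wait before MILD is therefore plausible, but its length is not visible.

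2. **What does the study procedure mean?** Two readings are open.
   - *MILD only.* Section 9 speaks of a procedure being aborted, which suggests an operation. On this reading the CMM-alone arm, 150 × 1/2 = 75 subjects (Sections 5.1 and 6.2), has no visible start. Nor does a MILD subject who is never treated.
   - *Assigned treatment in either arm.* Section 5.2 also speaks of CMM procedures. Table 2 in Section 7 lists physical therapy, nerve blocks and radiofrequency ablation beside MILD under a title about procedures. The text after the severity scale in Section 8.3 uses the plural for devices and procedures. On this reading each arm has a start, but it follows randomization and need not fall at the same time in both arms.

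   Both readings leave the interval from randomization to treatment outside the window.

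3. **Does that fit the other rules?**
   - Section 13.4: no. It covers SAEs during the study, and a randomized subject is in the study. Section 6.1 states the conditions under which "will the patient be officially enrolled into the study". The start of that sentence is not visible, so the exact moment is unknown, but Section 10.2 has eligibility confirmed before randomization.
   - Section 8.2: no direct conflict. It sets aside relatedness and is silent on timing.
   - Section 6.9: unclear. If its opening adjective governs both nouns, there is little conflict; otherwise there is one.
   - Section 9.2: tabulation by randomized group sits poorly with a start that can differ between those groups.

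4. **How large could it be?** The documents give neither an SAE rate nor an interval, so the following is illustration only.
   - Expected SAEs before MILD = 75 × annual rate × weeks / 52, and P(at least one) = 1 − exp(−expected).
   - Low: 0.05 per subject-year and 2 weeks give 75 × 0.05 × 2/52 = 0.14, or 13%.
   - Middle: 0.10 and 4 weeks give 75 × 0.10 × 4/52 = 0.58, or 44%.
   - High: 0.30 and 8 weeks give 75 × 0.30 × 8/52 = 3.46, or 97%.
   - An interval of zero gives zero.
   - At a constant rate, the share of first-year SAEs outside the window is weeks/52: 2/52 = 3.8% to 8/52 = 15.4%.

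   The spread reflects the assumptions and is not evidence about this trial.

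**The case against.** The strongest reply is that Section 8.5 read as a whole is less restrictive than its start sentence. It has subjects monitored during the study, has SAEs assessed at each visit, lets subjects report events at other times, and puts serious events on the CRF. That stands: a site has grounds to record an SAE before treatment. It also means that practice may vary, because the start sentence says otherwise.

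Second, starting at treatment matches the opening of Section 9, which evaluates treated subjects. This also stands in part. Leaving never-treated subjects out may be a deliberate choice of safety population, and a change to Section 8.5 alone would not bring them in. It does not remove the mismatch with tabulation by randomized group.

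Third, Section 8.4 and parts of Sections 5.2, 6.4.1, 6.5, 6.9 and 9.2 are not visible. They may define a CMM start, fix the interval to treatment, or already plan SAE tables by arm. This limits what can be said about the CMM arm. A CMM start given elsewhere would still not cover the time between randomization and MILD.

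A reader might infer three stronger things, none of which the documents support:
- *Half the trial has no SAE collection.* This requires the MILD-only reading, and the visit assessments in Section 8.5 show that CMM-arm events are expected.
- *SAEs will certainly be lost.* The interval may be zero, and sites may record the events anyway.
- *The rule favors MILD.* The direction depends on when each arm starts, and the CMM start is not visible.

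**Conclusion.** The concern holds in a limited form. Section 8.5 states a start that follows randomization, is not defined in the visible text, and may differ by arm. SAEs between randomization and treatment are outside that window on either reading of the term, which does not fit Section 13.4 or tabulation by randomized group.

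The number of events cannot be derived from the documents. The consequence is confined to the all-cause SAE and all-AE summaries and their comparability. The adjudicated endpoint counts serious events related to the device or procedure, so events before treatment hardly enter it. The primary ODI analysis does not use these data. This is a cheap improvement, held with medium confidence because relevant text is not visible.

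**What to change.** In Section 8.5, start collection of all SAEs and related AEs at randomization in both arms, and align Sections 13.4 and 6.9 with that sentence.

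If all-cause SAEs are summarized by arm, count them from randomization by randomized group. For that summary, also amend the opening sentence of Section 9 so that it covers all randomized subjects and not only those treated. Otherwise the new denominator would contradict it. The adjudicated endpoint in Section 9.2 stays as it is.

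The cost is a protocol amendment with IRB/EC approval under Section 13.6, at up to 20 centers, and modestly more AE data entry. No new visit is needed.
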